The protocol, informed consent form(s), recruitment materials, and all participant materials will be submitted to the Institutional Review Board (IRB) for review and approval. Approval of both the protocol and the consent form must be obtained before any participant is enrolled. Any amendment to the protocol will require review and approval by the IRB before the changes are implemented to the study. In addition, all changes to the consent form will be IRB-approved; a determination will be made regarding whether a new consent needs to be obtained from participants who provided consent, using a previously approved consent form.]

1 PROTOCOL SUMMARY

1.1 SYNOPSIS

Title:	The Menopause Transition: Estrogen Variability, HPA axis and Affective Symptoms
Study Description:	Women in the menopause transition ('perimenopause') are exposed to extreme hormone variability, tend to experience a unique set of severe stressors (e.g., divorce, death of loved ones), and are also at substantially elevated risk to suffer from mood and anxiety disorders. The purpose of this research is to understand the mechanisms by which variability in estradiol (E2) is associated with the symptoms of anxiety and anhedonia (loss of interest and pleasure - a common symptom of depression). By stabilizing E2 variability with a hormonal manipulation, this research will determine the degree to which the E2 variability (or E2 levels) plays a causal role in perimenopausal anxiety and anhedonia symptoms and whether it does so by affecting biological responses to stress.
Objectives:	
Primary Objectives:
 
1. Change over time in anxiety score from State-Trait Anxiety Inventory [Time Frame: Baseline (Week 8), Weeks 16, 20 and 24]2. Change over time in anhedonia score from the Snaith-Hamilton Pleasure Scale [Time Frame: Baseline (Week 8), Weeks 16, 20 and 24] 
Secondary Objectives:
 
1. Change over time in AUC cortisol stress response [Time Frame: Baseline (Week 8), Weeks 16, 20 and 24]2. Change over time in threat reactivity from Dot Probe behavioral task [Time Frame: Baseline (Week 8), Weeks 16, 20 and 24]

3. Change over time in measure of effort for motivation and anhedonia from Effort Expenditure for Reward Task [Time Frame: Baseline (Week 8), Weeks 16, 20 and 24]

Endpoints:

Primary Endpoints:

1. Change in STAI score [Time Frame: Baseline (Week 8), Weeks 16, 20 and 24]
2. Change in SHAPS score [Time Frame: Baseline (Week 8), Weeks 16, 20 and 24]

Secondary Endpoints:

1. Change in AUC cortisol response [Time Frame: Baseline (Week 8), Weeks 16, 20 and 24]
2. Change in “threat bias” score from Dot Probe task [Time Frame: Baseline (Week 8), Weeks 16, 20 and 24]
3. Change in “hard choice” score from EEfRT [Time Frame: Baseline (Week 8), Weeks 16, 20 and 24]

Study Population:

250 medically healthy female volunteers aged 45-60 undergoing natural menopause transition who meet STRAW+10 criteria for early or late menopause transition and are candidates for transdermal E2 and have had a normal mammogram in the previous 12 months.

Phase:

N/A

Description of Sites/Facilities Enrolling Participants:

Subjects are recruited from the area surrounding Chapel Hill, North Carolina and will be enrolled at the UNC-CH laboratory site located at [name]. Medical screening, including the gynecological exam and screening mammogram will occur at the UNC Medical Center on the UNC-CH campus. This study is not intended to include sites outside of the United States.

Description of Study Intervention:

Subjects randomized to the active treatment arm will wear a transdermal estradiol patch (0.1mg) every day for 16 weeks, changing the patch every 7 days. They will also take 200mg of micronized progesterone oral capsules every day for 12 days 8 weeks after randomization to estradiol and again at the end of the 16th week of randomization to estradiol. Subjects randomized to the placebo arm will follow the same regimen using matching placebo transdermal patches and placebo capsules.

Study Duration:

Enrollment will occur for approximately 54 months and data analysis will occur for 6 months following the close of enrollment. Estimated total study duration is 60 months.

Participant Duration:

Following medical screening, individual participation study duration is 6 months (24 weeks). Randomization to active/placebo treatment arm occurs at week 8, and subjects will be in the intervention phase for a total duration of 16 weeks.

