1.2 SCHEMA

Week 0

Medical Screening and Enrollment

- Obtain informed consent
- Screen potential participants by inclusion and exclusion criteria with online, phone, and medical screening via gynecological exam and mammogram
- Obtain history, document

Week 8

Lab Session- Baseline Assessments

- Administer STAI and SHAPS questionnaires
- Administer Dot Probe and EEfRT behavioral tasks
- Administer Trier Social Stress Test (TSST) and collect serum to measure cortisol at the end of baseline rest and at minutes 20, 30, and 45 of recovery post-TSST
- Urine HCG test to confirm subject is not pregnant prior to randomization

Randomization

- Active Intervention Group (0.10mg transdermal estradiol (E2))
- Placebo (matching inactive patch)
- Administer initial dose of study drug intervention

Week 16

Lab Session- Study Intervention, Side Effect & Compliance Checks

- Administer STAI and SHAPS questionnaires
- Administer Dot Probe and EEfRT behavioral tasks
- Administer Trier Social Stress Test (TSST) and collect serum to measure cortisol at the end of baseline rest and at minutes 20, 30, and 45 of recovery post-TSST
- Administer oral micronized progesterone (200mg daily)/matching placebo capsules for subjects to take for twelve days starting on Week 17 for the same treatment arms as E2/placebo randomization

Week 20

Lab Session- Study Intervention, Side Effect & Compliance Checks

- Administer STAI and SHAPS questionnaires
- Administer Dot Probe and EEfRT behavioral tasks
- Administer Trier Social Stress Test (TSST) and collect serum to measure cortisol at the end of baseline rest and at minutes 20, 30, and 45 of recovery post-TSST
- Continued administration of transdermal E2/placebo patch

Week 24

Final Lab Session- Study Intervention, Side Effect & Compliance Checks

- Administer STAI and SHAPS questionnaires
- Administer Dot Probe and EEfRT behavioral tasks
- Administer Trier Social Stress Test (TSST) and collect serum to measure cortisol at the end of baseline rest and at minutes 20, 30, and 45 of recovery post-TSST
- Administer oral micronized progesterone (200mg daily)/matching placebo capsules for subjects to take for twelve days starting on Week 25 for the same treatment arms as E2/placebo randomization
- Discontinue use of transdermal E2/placebo patch

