1.3 SCHEDULE OF ACTIVITIES (SOA)

Procedures	Medical Screening and Enrollment Week 0	Lab Session- Baseline Assessments & Randomization Week 8	Lab Session- Study Intervention, Side Effects, and Compliance Checks Week 16	Lab Session- Study Intervention, Side Effects, and Compliance Checks Week 20	Final Lab Session- Study Intervention, Side Effects, and Compliance Checks Week 24
Informed consent	X				
Demographics	X				
Medical history	X				
Physical and gynecological exam (including height and weight)	X				
Screening mammogram	X				
Pregnancy test ^a		X			
Randomization		X			
Administer transdermal estradiol/placebo		X	X	X	
Administer micronized progesterone/placebo			X		X
Discontinue transdermal estradiol/placebo					X
Administer STAI and SHAPS questionnaires		X	X	X	X
Administer Dot Probe and EEfRT behavioral tasks		X	X	X	X
Administer Trier Social Stress Test (TSST) and collect serum to measure cortisol ^b		X	X	X	X
Adverse event review and evaluation		X	X	X	X

a: urine pregnancy test (women of childbearing potential)
 b: serum collected at the end of baseline rest and at minutes 20, 30, and 45 of recovery post-TSST

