4.3 JUSTIFICATION FOR DOSE

By avoiding the first-pass metabolic effects of oral estrogen, transdermal E2 creates stable, premenopausal follicular phase E2 blood levels; and a physiologic profile of E2 relative to its metabolites estrone and estriol ¹³⁶⁻¹³⁸. Transdermal E2 also has a superior thromboembolic and metabolic safety profile than oral estrogen. ¹³⁹⁻¹⁴¹ A 7-day transdermal system provides significantly more stable concentrations and better patch adherence than twice weekly patches. ¹⁴² We have chosen (generic version) Climara® 7 day patches because the adhesive layer of the matrix distributes E2 molecules to continuously release E2, which is transported across skin leading to sustained levels of E2. ¹³⁶ Because of the dynamic changes in the reproductive axis during the MT and the possibility that, over 24 weeks, some women may transition from one STRAW stage to another, placebo will control for effects of reproductive aging, per se, on measures of interest and for habituation effects to repeat testing.

Progesterone Administration: To prevent E2-induced endometrial hyperplasia, women randomized to active E2 will take 200 mg micronized progesterone/day x 12 days during weeks 17-18 (after 2 months of drug intervention) and at the end of the study (weeks 25-26; after 4 months of drug intervention). Exposure to a progestin every 2 months is sufficient for endometrial protection. ¹⁴³ Under double-blind procedures, women randomized to placebo-E2 will take placebo P4; those randomized to active E2 will take active P4. We have chosen to give P4 in a discontinuous fashion instead of using Climara Pro® (a transdermal system that delivers both E2 and a progestin) because progestins antagonize E2 effects. ^{144,145}

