8.3.4 TIME PERIOD AND FREQUENCY FOR EVENT ASSESSMENT AND FOLLOW-UP

The study coordinator will monitor side effects and AEs related to the pharmacological E2 probe at all study visits (on a weekly basis initially and then monthly for two months) and report all side effects as well as any significant deterioration in anxiety or anhedonic symptoms (see below) directly to [name] following study visits. Side effects consistent with moderate or severe AEs or that are troublesome to the subject, or evidence of mood deterioration reported by telephone, will also be immediately reported to [name]. Based on the clinical skill required not only to assess but to act on emergent suicidality, a licensed clinical psychologist or psychiatry resident will conduct the suicide assessments at each laboratory session (weeks 8, 16, 20 and 24) or more frequently if indicated (e.g., every two weeks for those with a history of suicide intent). Investigator licensed clinical psychologist, [name], will oversee the fellows and residents in this responsibility.

Bleeding patterns and severity will be assessed at every study visit. Moreover, subjects will be instructed to contact us whenever they start a menstrual bleed. Staff will follow up to determine the amount and duration of bleeding. For any woman with profuse bleeding (defined as more than 3 tampons or pads for more than 5 days OR more than 1 tampon or pad per hour on any given day), [name] will be contacted, and she will decide whether to evaluate if clinically indicated. The timing of the bleeding with respect to the timing of the progesterone will contribute to that determination. Any unscheduled or prolonged bleeding (> 10 days) will be followed by an ultrasound or an endometrial biopsy or both. If ultrasound reveals the vaginal the stripe thickness to be more than 3 mm, then an endometrial biopsy will be performed. If the pathology report indicates hyperplasia, the subject will be withdrawn from the study, estrogen discontinued, and [name] will prescribe a stronger progestin. If the subject has hyperplasia, a follow-up biopsy would be performed at 3 months to make sure it is cured. The research study will pay for all biopsies required, including the follow-up biopsy.

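### The second capsule course falls in weeks 25-26, after the stated 24 weeks of participation and after the last scheduled adverse-event review

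*Combined protocol and SAP*

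**What the plan says.** **Participation and intervention.** Under Participant Duration, the synopsis (1.1) says "individual participation study duration is 6 months (24 weeks", with randomization at week 8, and "subjects will be in the intervention phase for a total duration of 16 weeks".

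**Capsules.** The schema (1.2) has the first course as "capsules for subjects to take for twelve days starting on Week 17" and the second as "capsules for subjects to take for twelve days starting on Week 25". Section 4.3 dates the second course "at the end of the study (weeks 25-26; after 4 months of drug intervention", and section 6.1.2 also gives weeks 25-26. Both arms follow this timetable, with progesterone in the active arm and placebo capsules in the other.

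**Patch.** It is stopped at week 24 (1.2, 1.3).

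**AE review.** The Schedule of Activities (1.3) marks "Adverse event review and evaluation" at weeks 8, 16, 20 and 24 and has no later column. Section 8.3.4 ties AE monitoring to all study visits, "on a weekly basis initially and then monthly for two months". Section 7.2, item 7, also refers to weekly visits before and after randomization, for headache monitoring in women with migraine. The schedule shows no weekly visits.

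**Completion.** Section 4.4 defines completion by the last visit or procedure in the Schedule of Activities.

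**Use of the AE data.** Sections 7.1 and 9.4.4 plan a two-sided Fisher exact test at alpha 0.05 every six months, comparing the arms on moderate or severe AEs, for the DSMB. Neither section says over what period a participant's events count.

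**The concern.** Study drug is taken after the study, as described in the synopsis and the schedule, has ended for the participant. Under section 4.4 a woman can count as having completed at week 24 with half of her capsule days still to come.

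The two courses are the same, but ascertainment after them is not: a scheduled AE review follows the first, and none follows the second. From week 24 the plan depends on participants reporting events on their own initiative, which usually yields less complete data than asking at a visit.

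The uncovered days also come directly after the patch is removed. The background (2.2) cites a study in which women with past perimenopausal depression had more symptoms, anxiety and anhedonia among them, within 1-3 weeks of abrupt estradiol withdrawal. Section 2.3.1, by contrast, says there is no evidence of clinically meaningful harm from stopping abruptly. Section 8.3.3.1 grades a rise in anxiety or anhedonia to clinically meaningful levels as a moderate AE, so such events belong in the Fisher test. Whichever view is right, data from these days bear on the question.

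Because the test has no stated window, whoever prepares each DSMB table must decide whether an event reported after week 24 counts.

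**Working it through.** **Inputs**
- Randomization at week 8 and a 16-week intervention phase (1.1).
- Two capsule courses of 12 days, starting in weeks 17 and 25 (1.2; weeks 17-18 and 25-26 in 4.3 and 6.1.2).
- Patch worn daily for 16 weeks and stopped at week 24 (1.1, 1.2).
- AE reviews at weeks 8, 16, 20 and 24 (1.3).
- Assumption: each visit falls at the end of its named week and each course starts on the first day of its named week. The week 24 visit is then day 24 × 7 = 168, and the second course starts on day 169.

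**1. The plan's own duration.** 8 + 16 = 24 weeks. The stated figure is reproduced, but only if the second capsule course is left out.

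**2. End of study-drug intake.** Last capsule day = 24 × 7 + 12 = day 180. 180 / 7 = 25.7 weeks from week 0, against a stated 24. 25.7 − 8 = 17.7 weeks after randomization, against a stated 16.

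**3. Share of capsule days with no later scheduled review.** Total = 2 × 12 = 24 days. After week 24 = 12 days. 12 / 24 = 50%.

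**4. Share of all study-drug days.** Patch days = 16 × 7 = 112, all before the week 24 review. The first course overlaps the patch and adds no days. Days on any study drug = 112 + 12 = 124. 12 / 124 = 9.7%.

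**5. The two courses compared.** The first ends on day 16 × 7 + 12 = 124, and the week 20 review (day 140) follows 16 days later. The second ends on day 180, and no review follows.

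**6. What under-reporting could cost.** Assume capsule-related events split evenly between the courses and that scheduled review captures all those in the first. Let c be the fraction of second-course events that participants report unprompted. Overall capture = (1 + c) / 2, which is 50% for c = 0, 75% for c = 0.5 and 100% for c = 1. The documents give no basis for choosing c.

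**7. Weekly visits (a separate matter).** The schedule has 3 post-baseline AE reviews (weeks 16, 20, 24). If weekly monitoring runs from week 9 to week 16, section 8.3.4 implies 8 + 2 = 10. If it covers only the first four weeks, it implies 4 + 3 = 7. Both readings are assumptions, and both exceed 3.

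**The case against.** The strongest reply is that no section stops AE collection at week 24 or excludes later events from the Fisher test. Unscheduled routes exist with no stated end date. Participants are told to contact the site whenever a menstrual bleed starts, and staff follow up on its amount and duration (8.3.4). Mood deterioration reported by telephone is passed on at once (8.3.4), and participant-initiated calls go to the DSMB (10.1.6). This stands. A reader might infer that the safety comparison misses half of the progesterone exposure; the documents support only that half of the capsule days have no later scheduled review.

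Three other inferences also go too far.
- *The loss is one-sided.* Both arms take capsules on the same timetable and have the same period without review. What is specific to the active arm is any drug-related excess arising in that period.
- *The missing weekly visits cause the gap.* On either reading above they fall in the first eight weeks on the patch, before the first capsules. Nor are they incompatible with the schedule: a site could hold them and also the listed lab sessions. The table is incomplete on this point, not contradictory.
- *The number of women affected can be found from the side-effect frequencies in 2.3.1.* Those figures carry no severity grade or duration and have no placebo rate subtracted, whereas the test counts only moderate or severe events.

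It can also be said that six calendar months are about 26.1 weeks (365.25 / 2 / 7), long enough to include the second course. The synopsis, however, specifies 24 weeks in the same phrase.

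None of this removes the conflict between capsules in weeks 25-26 and participation and scheduled review ending at week 24.

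**Conclusion.** The concern holds as an internal contradiction with a bounded effect on safety ascertainment. Study-drug intake runs to about day 180 (week 25.7), while stated participation and the last scheduled AE review end at week 24. This leaves 12 of 24 capsule days (50%), or 12 of 124 days on any study drug (9.7%), without a later scheduled review, and these are also the first days off the patch. All patch wear and the first capsule course are covered.

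Events in the uncovered period enter the DSMB tables and the Fisher test only if a participant reports them unprompted. A drug-related excess, if there is one, would arise in the active arm and could be under-captured. How much would be lost cannot be derived from the documents. The day counts rest on visits falling at the end of the named week; the contradiction itself does not depend on that assumption.

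The absence of the weekly visits from the schedule is a second, independent omission.

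**What to change.** 1. Reconcile sections 1.1 (Participant Duration), 1.2, 1.3, 4.3, 6.1.2, 7.2 and 8.3.4 so that the stated participation period and the scheduled AE collection cover every week in which study drug is taken. The completion definition in 4.4 refers to the Schedule of Activities and will follow it.
2. List in the Schedule of Activities the weekly visits that 7.2 and 8.3.4 describe, and say for which weeks they apply.
3. State in 7.1 and 9.4.4 that the AE window for the Fisher tests runs through the end of study-drug intake.

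The timing of the capsules and the form of any contact are for the investigators. The cost is a schedule and wording amendment and a brief AE contact after the last capsules.

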1.2 SCHEMA

Week 0

Medical Screening and Enrollment

- Obtain informed consent
- Screen potential participants by inclusion and exclusion criteria with online, phone, and medical screening via gynecological exam and mammogram
- Obtain history, document

Week 8

Lab Session- Baseline Assessments

- Administer STAI and SHAPS questionnaires
- Administer Dot Probe and EEfRT behavioral tasks
- Administer Trier Social Stress Test (TSST) and collect serum to measure cortisol at the end of baseline rest and at minutes 20, 30, and 45 of recovery post-TSST
- Urine HCG test to confirm subject is not pregnant prior to randomization

Randomization

- Active Intervention Group (0.10mg transdermal estradiol (E2))
- Placebo (matching inactive patch)
- Administer initial dose of study drug intervention

Week 16

Lab Session- Study Intervention, Side Effect & Compliance Checks

- Administer STAI and SHAPS questionnaires
- Administer Dot Probe and EEfRT behavioral tasks
- Administer Trier Social Stress Test (TSST) and collect serum to measure cortisol at the end of baseline rest and at minutes 20, 30, and 45 of recovery post-TSST
- Administer oral micronized progesterone (200mg daily)/matching placebo capsules for subjects to take for twelve days starting on Week 17 for the same treatment arms as E2/placebo randomization

Week 20

Lab Session- Study Intervention, Side Effect & Compliance Checks

- Administer STAI and SHAPS questionnaires
- Administer Dot Probe and EEfRT behavioral tasks
- Administer Trier Social Stress Test (TSST) and collect serum to measure cortisol at the end of baseline rest and at minutes 20, 30, and 45 of recovery post-TSST
- Continued administration of transdermal E2/placebo patch

Week 24

Final Lab Session- Study Intervention, Side Effect & Compliance Checks

- Administer STAI and SHAPS questionnaires
- Administer Dot Probe and EEfRT behavioral tasks
- Administer Trier Social Stress Test (TSST) and collect serum to measure cortisol at the end of baseline rest and at minutes 20, 30, and 45 of recovery post-TSST
- Administer oral micronized progesterone (200mg daily)/matching placebo capsules for subjects to take for twelve days starting on Week 25 for the same treatment arms as E2/placebo randomization
- Discontinue use of transdermal E2/placebo patch

1.3 SCHEDULE OF ACTIVITIES (SOA)

Procedures	Medical Screening and Enrollment Week 0	Lab Session- Baseline Assessments & Randomization Week 8	Lab Session- Study Intervention, Side Effects, and Compliance Checks Week 16	Lab Session- Study Intervention, Side Effects, and Compliance Checks Week 20	Final Lab Session- Study Intervention, Side Effects, and Compliance Checks Week 24
Informed consent	X				
Demographics	X				
Medical history	X				
Physical and gynecological exam (including height and weight)	X				
Screening mammogram	X				
Pregnancy test ^a		X			
Randomization		X			
Administer transdermal estradiol/placebo		X	X	X	
Administer micronized progesterone/placebo			X		X
Discontinue transdermal estradiol/placebo					X
Administer STAI and SHAPS questionnaires		X	X	X	X
Administer Dot Probe and EEfRT behavioral tasks		X	X	X	X
Administer Trier Social Stress Test (TSST) and collect serum to measure cortisol ^b		X	X	X	X
Adverse event review and evaluation		X	X	X	X

a: urine pregnancy test (women of childbearing potential)
 b: serum collected at the end of baseline rest and at minutes 20, 30, and 45 of recovery post-TSST

